**Estimand for secondary safety objective:**

The estimand attributes for the secondary safety objectives are as follows:

**Population:**

- The population is female participants aged  $\geq 12$  years with suspected uUTI.

**Endpoints:**

The safety endpoints are Adverse Events (AE), Serious Adverse Events (SAE) and Adverse Events of Special Interests (AESI).

**Treatment condition:**

- The treatment condition is Gepotidacin 1500 mg BID

**Intercurrent Event and Strategy:**

The intercurrent event and estimand strategy is:

- Study treatment discontinuation due to any reason (treatment policy).

**Population level summary**

- The population-level summary to be estimated are counts and percentages of participants who have experienced AEs, SAEs, and AESIs.

**Rationale of estimands supporting secondary safety objectives:**

Interest lies in assessing safety of participants irrespective of whether they completed the study intervention or not. These safety endpoints will be captured and reported for each participant after the first dose of treatment regardless of study treatment completion.

## 1.2. Study Design

Overview of Study Design and Key Features

The study design schematic is shown below in Figure 1

## Overview of Study Design and Key Features

**Figure 1** Study design overview

<pre> graph LR     V1[Visit 1 (Baseline/Day 1)a (Onsite)] --> S1[Eligibility: - Female participants - ≥12 years of age - CSS ≥2 total score - Nitrite or pyuria (presence of 3+/large leukocyte esterase) from a pretreatment clean-catch midstream urine sample]     S1 --> SI[Study Intervention: Gepotidacin 1500 mg orally BID for 5 daysb]     SI --> OTV[On-treatment Visits (Visit 2, Visit 3, Visit 4, and Visit 5) (Telephone)]     OTV --> V6[Visit 6 CCI (Telephone) Safety follow-up and CSSc]     V6 --> V7[Visit 7 (Follow-up/Day 28±3) (Telephone) Safety follow-up]   </pre>	
	
a. During Visit 1, prior to first dose of study intervention, the Virtual Research Coordination Center (VRCC) will contact the participant by telephone to perform the CSS assessment and CCI CCI (in that specific order). This will be used as the Baseline CSS. The CSS will be reviewed (but not remeasured) by a study physician or otherwise appropriate medically trained staff from the study site onsite along with determination of whether other eligibility criteria are met before the first dose of study medication. Only If VRCC cannot do the telephone call, then the study physician or otherwise appropriate medically trained staff from the study site will ask the CSS questions and complete the CCI CCI before the first dose of study intervention. Only one CSS and CCI is to be performed at Visit.
 
b. The first dose of study intervention will be administered at the study site during Visit 1; the remaining 9 doses over the 5-day treatment course will be self-administered as outpatients. Each dose is to be taken after food consumption and with water to assist with tolerability.
 
c. At Visit 2, Visit 3, Visit 4, and Visit 5, the CSS assessment and CCI CCI will be completed (in that order) by VRCC. CCI CCI

Design Features	
Phase 3b, open-label, single-arm, multicentre study to evaluate clinical symptom improvement and the safety of gepotidacin during the treatment of uUTIs. Female participants need to be ≥12 years of age with 2 or more clinical symptoms of uUTI and nitrite or pyuria from a pre-treatment clean-catch midstream urine sample.
 
The total duration of study participation is approximately 28 days, with at least 1 planned onsite study visit and 6 telephone calls study contacts, with allowance for unscheduled visits.
 
Visit Baseline/Day 1): onsite, Visit 2 (24 hours ±4 hours), Visit 3 (48 hours ±4 hours), Visit 4 (72 hours ±4 hours), and Visit 5 (96 hours ±4 hours): telephone, Visit 6 (CCI): telephone, Visit 7 (Follow-up/Day 28): telephone, Unscheduled Visit: onsite or telephone.
 
Approximately 90 participants will be enrolled in the study to ensure at least 82 evaluable participants are included in the primary analysis.
 
Each visit will be assessed over a 24-hour period, beginning with the first dose of study intervention received for an individual participant. For example, participants who only receive 1 dose of study intervention on their first calendar day in the study due to a late afternoon/evening Visit 1 will take the second dose

Overview of Study Design and Key Features	
	on the following calendar day, which will complete Day 1. This pattern will continue until all 10 doses are received; thus, the tenth/last dose will be taken prior to Visit 5 (may be 5 or 6 calendar days, depending on when the first dose is taken). The primary uUTI symptom assessment will be the CSS at 24 hours $\pm$ 4 hours (Visit 2). Participants must have taken a total of 2 doses of gepotidacin before the 24 hours $\pm$ 4 hours (Visit 2) assessment of CSS. Other uUTI assessments will include the [REDACTED] [REDACTED]
Study intervention	Participants will receive oral study intervention BID for 5 days. Doses are to be taken approximately 12 hours apart, but the allowable window is 6 to 14 hours and must be at least a 6-hour minimum window between doses. The first oral dose will be administered at the study site at Baseline; participants will self-administer subsequent doses as outpatients thereafter.
Study intervention Assignment	Participants will be receiving the following study treatment once passed eligibility criteria as described in Figure 1 Gepotidacin: 1500 mg (2 $\times$ 750 mg) administered orally twice daily (BID) for 5 days to complete 3000 mg total daily dose.
Interim Analysis	An Interim Analysis (IA) is not planned in the study.

## 2. STATISTICAL HYPOTHESES

No formal hypothesis testing will be performed for the primary, secondary, and exploratory endpoints.

### 2.1. Multiplicity Adjustment

No multiplicity adjustment will be performed for the primary, secondary, and exploratory endpoints.

### 3. ANALYSIS SETS

Analysis Set	Definition / Criteria	Analyses Evaluated
Screened (SCR)	
 
• All participants who were screened for eligibility
 
	
 
• Study population
 

Intent to-treat (ITT)	
 
• All participants who enrolled in the study (i.e., excluding screen failures).
 
	
 
• Study population
 
• Summary for disclosure documentation
 
• CCI [REDACTED] CCI [REDACTED]
 
• Supplementary estimand of the primary endpoint as described in Section 1.1.
 
• Supplementary estimands for secondary efficacy endpoints as described in Section 1.1. (Clinical Improvement at 48 hours (<math>\pm 4</math> hours), 72 hours (<math>\pm 4</math> hours), 96 hours (<math>\pm 4</math> hours) and Clinical Resolution at 24 hours (<math>\pm 4</math> hours), 48 hours (<math>\pm 4</math> hours), 72 hours (<math>\pm 4</math> hours), 96 hours (<math>\pm 4</math> hours))
 

Primary Clinically Evaluable at 24 hours ( $\pm 4$ hours) (CE24)	
 
• All participants in the ITT analysis set who adhered to the 2 doses of treatment as prescribed before the 24 hours (<math>\pm 4</math> hours) CSS assessment (if available), or, before 24 hours (+4 hours) from first dose (if CSS assessment is missing).
 
	
 
• Primary estimand for primary efficacy endpoint as described in Section 1.1. (Clinical Improvement at 24 hours (<math>\pm 4</math> hours))
 
• Estimands for secondary efficacy endpoints as described in Section 1.1. (Clinical Improvement at 24 hours (<math>\pm 4</math> hours))
 

Clinically Evaluable at 48 hours ( $\pm 4$ hours) (CE48)	
 
• All participants in the ITT analysis set who adhered to at least 80% of planned doses of gepotidac in as prescribed before the 48 hours (<math>\pm 4</math> hours) CSS assessment (if available), or, before 48 hours (+4 hours) from first dose (if CSS assessment is missing).
 
	
 
• Estimands for secondary efficacy endpoints as described in Section 1.1.
 
• (Clinical Improvement and Clinical Resolution at 48 hours (<math>\pm 4</math> hours))
 

Clinically Evaluable at 72 hours	
 
• All participants in the ITT analysis set who adhered to at least 80% of planned doses of gepotidac in as
 
	
 
• Estimands for secondary efficacy endpoints as described in Section 1.1.
 

Analysis Set	Definition / Criteria	Analyses Evaluated
( $\pm 4$ hours) (CE72)	prescribed before the 72 hours ( $\pm 4$ hours) CSS assessment (if available), or, before 72 hours ( $+4$ hours) from first dose (if CSS assessment is missing).	
 
(Clinical Improvement and Clinical Resolution at 72 hours (<math>\pm 4</math> hours))
 

Clinically Evaluable at 96 hours ( $\pm 4$ hours) (CE96)	
 
All participants in the ITT analysis set who adhered to at least 80% of planned doses of gepotidacin as prescribed before the 96 hours (<math>\pm 4</math> hours) CSS assessment (if available), or, before 96 hours (<math>+4</math> hours) from first dose (if CSS assessment is missing).
 
	
 
Estimands for secondary efficacy endpoints as described in Section 1.1. (Clinical Improvement and Clinical Resolution at 96 hours (<math>\pm 4</math> hours))
 
CC1
 

CC1		
 
•
 

Safety (SAF)	
 
All enrolled participants who received at least 1 dose of study intervention.
 
	
 
Estimand for secondary safety endpoints as described Section 1.1.
 

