Objectives, endpoints, and estimands: The primary objective of this study is to evaluate the clinical symptom improvement with gepotidacin treatment in female participants with uUTI at (24 hours [± 4 hours]). This will be evaluated by the number of participants who achieve clinical symptom improvement (without the need for other systemic antimicrobials), defined as a decrease from Baseline in CSS total score of at least 1 point at (24 hours [± 4 hours]). For additional information on the primary, secondary, and exploratory objectives and endpoints, refer to Section 3.

[figure not shown]
Overall design: This is a Phase 3b, open-label, single-arm, multicenter study to evaluate clinical symptom improvement and the safety of gepotidacin in female participants ≥ 12 years of age with clinical symptoms and urine dipstick findings suggestive of uUTI. Participants who meet eligibility requirements will receive gepotidacin 1500 mg administered orally as 2×750 mg tablets BID for 5 days. (Note: Each dose is to be taken after food consumption and with water to assist with tolerability.) Clinical symptom and safety assessments will be conducted throughout the study. The total duration of study participation is approximately 28 days, with at least 1 planned on site study visit and 6 telephone call study contacts (see Section 1.3 and Section 8 for study visit details), with allowance for unscheduled visits. For additional information on the overall design, refer to Section 4.1.

Number of participants: Approximately 90 participants will be enrolled in the study to ensure at least 82 evaluable participants are included in the primary analysis, such that the half width of the 95% CI is approximately $\leq 10\%$, under an assumption that 74% of participants meet the primary endpoint criteria as observed in the Phase 3 studies.

Data monitoring/other committee: This will be overseen by the GSK SRT (Section 10.9.6).

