7. DISCONTINUATION OF STUDY INTERVENTION AND PARTICIPANT DISCONTINUATION/WITHDRAWAL

7.1. Discontinuation of study intervention

Participants may voluntarily discontinue study intervention at any time. The investigator may also, at his or her discretion, discontinue the participant from study intervention at any time and initiate appropriate alternative therapy.

The primary reason for premature discontinuation of study intervention will be documented in the eCRF based on the list below:

- Adverse event
- Protocol deviation
- Termination of the study by GSK
- Lost to follow-up
- Investigator discretion
- Lack of efficacy
- Pregnancy
- Study site terminated by sponsor
- Withdrawal by participant
- Participant reached protocol-defined stopping criteria

- Other (specify)
- Death

Participants who discontinue study intervention for the reasons above will not be considered withdrawn from the study and should participate in all subsequent study visits (see Section 1.3).

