### **Rationale of estimand for primary endpoint:**

1. Interest lies in evaluating study intervention benefit through a decrease in CSS total score in participants who achieve 100% compliance to study intervention (by taking the 1500 mg ( $2 \times 750$  mg) dose orally twice daily (BID) as prescribed) before the CSS assessment at 24 hours ( $\pm 4$  hours).
2. Participants who take other antimicrobials for uUTI indicate lack of treatment benefit and will not be able to achieve symptom improvement (i.e., treatment failures). Participants who take other antimicrobials for other infections might confound the outcome by improving the symptoms. Therefore, such participants are also set to treatment failures.

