#### 4.2.2. Main analytical approach for primary endpoint

Participants achieving the primary efficacy endpoint of clinical symptom improvement with resolution at 24 hours  $\pm 4$  hours (refer definition in Section [4.2.1.](#)) will be estimated by frequency and percentage using CE24 set.

Exact Binomial (Clopper Pearson) 95% confidence limits for percentage of participants with clinical symptom improvement at 24 hours  $\pm 4$  hours will be computed. Participants who are not able to complete the CSS assessment at 24 hours ( $\pm 4$  hours) will be considered as 'treatment failure' and included as 'not improvers' in primary analysis.

A stacked bar graph will be produced for:

- Individual component of clinical symptoms by severity. (none/mild/moderate/severe) at 24 hours and baseline which will be presented using the ITT and CE24 sets respectively.
- Total clinical symptom score categories classified as (<2, 2-5, 6-8, 9-12) will be presented by visits using the ITT and CE24 sets.

- Percentage of participants with clinical improvement, clinical resolution, Clinical worsening and UTD by visits for CE24 set.

A descriptive summary will be presented for CSS total and individual scores (Dysuria, Frequency, Urgency, and Lower abdominal or Suprapubic pain) including n, mean, standard deviation (std), median, minimum, and maximum at each timepoint (24 hours  $\pm$  4 hours, 48 hours  $\pm$  4 hours, 72 hours  $\pm$  4 hours and 96 hours  $\pm$  4 hours) for the ITT set. Participants listings for clinical outcome and response will also be produced for ITT set.

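### At 48, 72 and 96 h the 80% dose rule can remove participants whom the SAP defines as failures because they were switched to another antibiotic for uUTI

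*SAP*

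**What the plan says.** **Failure rule.** SAP 1.1 applies a composite strategy to other antimicrobials at every timepoint. Its rationale for the primary endpoint reads "Participants who take other antimicrobials for uUTI indicate lack of treatment benefit and will not be able to achieve symptom improvement (i.e., treatment failures"), and the secondary rationale repeats the idea for improvement and resolution. SAP Table 1 classes a participant who received another systemic antimicrobial for uUTI on or before a timepoint as Clinical Worsening. A switch therefore counts as a failure at every later timepoint too.

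**Discontinuation rule.** For the secondary estimands, SAP 1.1 handles stopping study drug for any reason by treatment policy. Protocol 7.1 keeps such participants in the study and expects them at all later visits.

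**Evaluability rule.** SAP 4.2.2 and 4.3.1.2 run the main analyses on the CE sets of SAP Section 3. CE24 takes "All participants in the ITT analysis set who adhered to the 2 doses of treatment as prescribed before the 24 hours" assessment. CE48, CE72 and CE96 take those at or above 80%; for CE96, those "who adhered to at least 80% of planned doses of gepotidacin as prescribed before the 96 hours" assessment. The definitions make no exception for a participant switched to another antibiotic.

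**Link between the rules.** Protocol 7.1 lets the investigator "discontinue the participant from study intervention at any time and initiate appropriate alternative therapy". The Schedule of Activities notes and Protocol Section 8 allow an alternative antibiotic at an Unscheduled Visit, including one held for lack of response.

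**The concern.** Three strategies meet in one participant. The composite strategy wants her in the denominator as a failure, treatment policy wants her followed regardless of stopping, and the dose rule takes her out. The dose rule acts first because it decides who is in the table at all.

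The participants affected are among the clearest treatment failures. The study exists to describe improvement and resolution day by day. If the denominator sheds rescued participants between 48 and 96 h, part of any rise in the curve can come from who is counted and not from who improved. The same participant can be a failure at one visit and missing from the next.

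**Working it through.** **The plan's own figure.** Protocol 1.1 sets the target: "Approximately 90 participants will be enrolled in the study to ensure at least 82 evaluable participants are included in the primary analysis". The precision aim there is an interval half-width of no more than about 10 points, at a rate of 74% taken from the Phase 3 studies. SAP 4.2.2 specifies "Exact Binomial (Clopper Pearson) 95% confidence limits for percentage of participants with clinical symptom improvement". The half-width is (upper − lower)/2 of the Clopper-Pearson interval at x = 0.74n. For n = 81 it is 10.03 points and for n = 82 it is 9.97, so 82 is reproduced. The plan leaves 90 − 82 = 8 places (8.9%) for non-evaluable participants.

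**Inputs and assumptions.** Doses are about 12 h apart with a 6 to 14 h window (Protocol 6.1; SAP 1.2). I assume strict 12 h spacing, so dose k falls at 12(k − 1) h. I assume that gepotidacin stops at the switch, and that the compliance denominator is all doses planned up to the timepoint (the formula in SAP 6.1.6 is redacted). By 96 h that is 8 doses at 12 h spacing, or 10 on the statement in Protocol 6.1 that the last dose precedes Visit 5. At 12 h spacing dose 10 would fall at 12 × 9 = 108 h. The two must be reconciled; both are carried here.

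**Doses needed to stay in each set** (required share × planned, rounded up):

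| Set | Planned | Needed | Time of that dose | Switches lost |
|---|---|---|---|---|
| CE24 | 2 | 2 | 12 h | before about 12 h |
| CE48 | 4 | 4 (3/4 = 75%) | 36 h | before about 36 h |
| CE72 | 6 | 5 (4/6 = 67%) | 48 h | before about 48 h |
| CE96 | 8 | 7 (6/8 = 75%) | 72 h | before about 72 h |
| CE96 | 10 | 8 (7/10 = 70%) | 84 h | before about 84 h |

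**One participant, switched at 40 h after 4 doses.** 48 h: 4/4 = 100%, in the set, a failure. 72 h: 4/6 = 67%, out. 96 h: 4/8 = 50% or 4/10 = 40%, out either way.

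**Direction.** A dropped switcher is a failure by definition. Let p be the composite rate with all such participants kept and s the share dropped. The CE rate is then p/(1 − s), which is never below p. At s = 5% the excess is 2.6 points for p = 50%, 3.9 for p = 74% and 4.7 for p = 90%.

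**Illustration at the later visits (the counts are assumed).** 82 in CE48, 70 improved, 4 switched at 40 h: 70/82 = 85.4% (exact 95% CI 75.8 to 92.2). At 96 h, with the same 70 improved and the 4 dropped: 70/78 = 89.7% (80.8 to 95.5). That is a rise of 4.4 points with no further improvement.

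**Primary endpoint.** Start from 61/82 = 74.4% (63.6 to 83.4) and put back k participants dropped for a switch before dose 2:

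| k | Rate | Change (points) |
|---|---|---|
| 1 | 61/83 = 73.5% | −0.9 |
| 2 | 61/84 = 72.6% | −1.8 |
| 4 | 61/86 = 70.9% | −3.5 |
| 8 | 61/90 = 67.8% | −6.6 |

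The last row is an outer bound: it supposes that every place in the non-evaluable allowance went to a participant switched before dose 2.

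**The case against.** **The restriction to adherers is declared.** SAP 1.1 names a principal stratum strategy and defines the populations as women able to take 2 doses, or at least 80%. At 24 h this largely stands: a participant without dose 2 is outside the stated population, and the primary estimand lists no treatment-policy strategy for stopping. At 48 to 96 h it does not settle the matter, because the same estimand also promises treatment policy for discontinuation. Missed doses that follow from a switch for lack of response also do not show that the participant was unable to comply.

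**The link is inferred.** No passage says that gepotidacin must stop at a switch. Protocol 7.1 describes a discretionary action, and the Unscheduled Visit text is silent. This stands as an assumption.

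**Parts of the SAP are redacted.** The compliance formula, one row of the analysis-set table and an added supplementary analysis cannot be read. Whether they bear on this is unknown.

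**Other outputs exist.** The ITT supplementary analyses (SAP 4.2.4 and 4.3.1.4) would count these participants as failures, but they run only above a redacted non-compliance threshold. ITT score summaries, ITT outcome listings and shift tables, an intercurrent-event table and reasons for exclusion are planned without that condition. The participants therefore remain visible, but these outputs do not correct the headline rates. The primary multiple-imputation analysis uses CE24 and does not bring them back.

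**Keeping only switchers is asymmetric.** Participants who improve and stop early would still be dropped, so selection would depend partly on outcome and could push rates down. This is fair, and is the reason for pairing the retention rule with an unconditional ITT analysis.

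**Conclusion.** The point holds for 48, 72 and 96 h. The composite and treatment-policy strategies conflict with the 80% dose rule, and no visible text gives precedence. Relative to the SAP's own failure definition the resulting error is zero or upward. This rests on gepotidacin stopping at the switch, 12 h spacing, and a denominator of all doses planned up to the timepoint. The 96 h cut-off moves between about 72 and 84 h with the planned dose count.

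The size cannot be determined, since no switch rate is given; the 4.4-point example shows the mechanism and is not a forecast.

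A reader might infer that every switched participant is deleted, that the later rates will rise for this reason, or that the primary result is materially inflated. The documents do not support these readings. Switches after the required dose stay in the set as failures. A rise is possible, not established. At 24 h only a switch between the supervised first dose and dose 2 (due 6 to 14 h later) is lost. The effect on the primary rate is therefore probably small, about 0.9 points per participant against a half-width of about 10.

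**What to change.** 1. Add to the CE definitions in SAP Section 3: *Participants who received another systemic antimicrobial for uUTI on or before a timepoint are kept in that and all later CE sets and counted as not improved / not resolved, whatever number of gepotidacin doses was taken.*
2. Align the estimand populations in SAP 1.1 with this. The secondary population is limited to those who can comply with at least 80% of doses. The SAP's supplementary secondary population carries the same limit, although its analysis is on ITT and Protocol Section 3 does not impose it there.
3. Run the ITT supplementary analyses in SAP 4.2.4 and 4.3.1.4 unconditionally. They treat switched and other non-adherent participants alike.
4. Reconcile the planned dose count before Visit 5, so that the CE96 denominator is fixed before database lock.

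Cost: a few sentences of SAP text, one programming flag and a small amount of extra analysis. Reported rates may be slightly lower. No clinical rule changes.

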## 4. STATISTICAL ANALYSES

### 4.1. General Considerations

The purposes of statistical analysis to estimate the percentage of participants showing an improvement/resolution of the clinical symptoms and safety and tolerability with gepotidacin treatment in female participants with uUTI.

Statistical analysis will be presented as per estimands for primary and secondary objectives. ICEs and strategies for primary and secondary estimands are defined in Section 1.1.

The following variables are:

- Age (continuous and ordered categorically)
- Race (categorical).
- Ethnicity (categorical).
- Site (categorical).

Any variable or combinations of variables which leads to a non-zero count (n) of <11 participants in a clinical study having this mix of characteristics must be considered as a risk to re-identification.

